6.6. Continued Access to Study Intervention After the End of the Study

As this is a FIH clinical trial, no post-trial study intervention is currently planned to be provided to study participants at the end of the study. Depending on the overall development path, the sponsor will make an effort to provide post-trial study intervention to appropriate participants who are tolerating treatment and continuing to experience clinical benefit.

6.7. Treatment of Overdose

For this study, any dose of PF-07265028 any dose greater than the assigned dose within a 24-hour time period will be considered an overdose.

Sponsor does not recommend specific treatment for an overdose.

In the event of an overdose, the investigator/treating physician should:

1. Contact the medical monitor within 24 hours.
2. Closely monitor the participant for any AEs/SAEs and laboratory abnormalities for at least 5 half-lives or 28 calendar days after the overdose of PF-07265028 (whichever is longer).
3. Document the quantity of the excess dose as well as the duration of the overdose in the CRF.
4. Overdose is reportable to Pfizer Safety **only when associated with an SAE**.
5. Obtain a blood sample for PK analysis within 7 days from the date of the last dose of study intervention if requested by the medical monitor (determined on a case-by-case basis).

Decisions regarding dose interruptions or modifications will be made by the investigator in consultation with the medical monitor based on the clinical evaluation of the participant.

6.8. Concomitant Therapy

All prior and concomitant treatments, received by participants from 30 days prior to screening and up to 30 days after the last dose of study treatment, or up to the start of new anti-cancer therapy, including supportive care drugs (eg, antiemetic treatment and prophylaxis), drugs used to treat AEs or chronic diseases, and nondrug supportive interventions (eg, transfusions) will be recorded on the CRF. Concomitant medications for AEs and SAEs should follow respective guidance for the AE and SAE reporting period.

Hormonal contraceptives that meet the requirements of this study are allowed to be used in participants who are WOCBP (see [Appendix 4](#)).

Concomitant treatment considered necessary for the participant's well-being may be given at discretion of the treating physician.

Prohibited therapies and concomitant therapy instructions during the study are listed in this section and in the sub-study appendices. If there is a clinical indication for 1 of the medications specifically prohibited during the study, discontinuation from the study treatment may be required. Participants may receive other medications that the investigator deems to be medically necessary. The final decision on any supportive therapy rests with the Investigator and/or the participant's primary physician. The decision to continue the participant in the study requires mutual agreement of the investigator, the sponsor and the participant.

Any questions regarding administration of concomitant medications should be directed to the sponsor.

6.8.1. Potential Drug-Drug Interactions

Inhibition of CYP3A4/5 isoenzymes may increase PF-07265028 exposure leading to potential increases in toxicities. Induction of CYP3A4/5 isoenzymes may decrease PF-07265028 exposure leading to potential decrease in efficacy. Therefore, the use of food (eg, grapefruit juice), supplements (eg St John's Wort), or drugs (eg ketoconazole) that are known strong and/or moderate CYP3A4 inhibitors, or strong CYP3A4 inducers is prohibited within 10 days or 5 half-lives of the CYP3A4 inhibitor/inducer (whichever is longer) prior to the first dose of study intervention. Please see [Appendix 9](#) for a comprehensive drug list.

Concomitant use of PF-07265028 and a substrate of CYP3A4, CYP2D6, UGT1A1, P-gp or BCRP may increase the systemic exposure of that substrate. Therefore, concomitant use of PF-07265028 with sensitive substrates with NTI for CYP3A4, CYP2D6, UGT1A1, P-gp, and highly sensitive substrates for BCRP is prohibited.

For HMG CoA reductase inhibitors (statins): Atorvastatin (limit dose to 10 mg daily), fluvastatin (limit dose to 20 mg daily), rosuvastatin (limit dose to 5 mg daily), simvastatin (avoid usage).

Please see [Appendix 8 Section 10.8](#) for a comprehensive list for prohibited drugs or use with caution due to DDI.

6.8.2. Other Prohibited and/or Limited use of Anti-tumor/Anti-Cancer or Experimental Drugs, or Procedures

Prior systemic anti-cancer therapy within 14 days (6 weeks for mitomycin C or nitrosoureas) prior to study treatment are excluded.

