2.2.6. Nonclinical Pharmacokinetics and Metabolism

Details of the nonclinical ADME properties of PF-07265028 are provided in the PF-07265028 IB.

The predicted human plasma clearance and volume of distribution of PF-07265028 are 5 mL/min/kg and 5 L/kg respectively, with an effective half-life of 12 hours. High to complete absorption following oral administration is expected, with an estimated oral bioavailability of 56% at the predicted efficacious dose of 140 mg QD.

The major route of clearance for PF-07265028 is predicted to be CYP3A4-mediated oxidative metabolism, with minor contributions from CYP3A5, 2D6, 2J2, and 1A1 ($f_{m, CYP3A} = 0.80$). No human-specific metabolite was observed in hepatocytes or liver microsomes.

Human plasma protein-binding was measured, with a fraction unbound of 0.0674. Human blood-to-plasma ratio was measured, with a ratio of 1.1.

PF-07265028 is a potential perpetrator of DDIs by time-dependent inhibition of CYP2D6, reversible inhibition of CYP3A, UGT1A1, and transporter-mediated inhibition of P-gp, BCRP, and OCT1 at the clinically relevant dose of 140 mg QD. Potentially, UGT1A9 and MATE2K could also be inhibited at higher doses of PF-07265028. In isolated human hepatocytes treated with PF-07265028, no significant induction of CYP1A2 was observed; however, a concentration-dependent downregulation of CYP3A4 and CYP2B6 mRNA and enzyme activity was observed, and the potential for induction of these enzymes in cells could not be determined.

PF-07265028 was highly permeable in RRCK cells, with an apparent permeability of $\sim 9 \times 10^{-6}$ cm/s. PF-07265028 is a substrate of MDR1 (P-gp) and BCRP efflux transporters with low apical-to-basolateral permeability ($P_{app,AB}$) and high ERs in MDCK-MDR1 (NIH) cells ($P_{app,AB}$ of 0.29×10^{-6} cm/s and ER of 110) and MDCK-hBCRP cells ($P_{app,A-B}$ of 1.1×10^{-6} cm/s and ER of 31.9). PF-07265028 is not a substrate of OCT1 in vitro.

Since the absorption in human is predicted to be high, and the predominant clearance mechanism is expected to be via metabolism, the potential risk of DDIs due to transporter inhibition for PF-07265028 as a victim is low.

Based on GastroPlus simulations, the oral absorption of PF-07265028 is not anticipated to be sensitive to stomach pH changes.

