17. Concomitant use or anticipated need for food (eg grapefruit juice), supplements (eg, St John's Wort), or drugs (eg, ketoconazole) that are known strong and/or moderate CYP3A4 inhibitors, or strong CYP3A4 inducers, including their administration within 10 days or 5 half-lives of the CYP3A4 inhibitor/inducer (whichever is longer) prior to the first dose of study intervention. Please see [Section 10.8](#) for a comprehensive drug list.
18. Concomitant or anticipate use of sensitive substrates with NTI for CYP3A4, CYP2D6, UGT1A1, P-gp, and highly sensitive substrates for BCRP. Please see [Section 10.8](#) for a comprehensive drug list.
19. Receipt of a live vaccine within 30 days of enrollment.

20. Current use of any prohibited concomitant medication(s) or those unwilling/unable to use a permitted concomitant medication(s). Refer to [Section 6.8 Concomitant Therapy](#).
21. Transfusion of RBCs or platelets or administration of hematopoietic growth factors within 2 weeks of C1D1.

Prior/Concurrent Clinical Study Experience:

22. Participation in other studies involving investigational drug(s) within 4 weeks or 5 half-lives (whichever is shorter) prior to planned first dose. Cases must be discussed with sponsor's medical monitor to judge eligibility.

Diagnostic Assessments:

23. Serum or urine pregnancy test (for WOCBP) positive at screening.
24. While SARS-CoV2 testing is not mandated for entry into this protocol, testing should follow local clinical practice standards. If a participant has a positive test result for SARS-CoV2 infection, is known to have asymptomatic infection, or is suspected of having SARS-CoV2, he/she is excluded. See [Section 10.10](#) for more information around SARS-CoV2
25. HBV, HCV, known HIV- or AIDS related illness. This protocol excludes participants with active infections but permits inclusion of participants who meet the following conditions:
 - Human immunodeficiency virus (HIV) infected participants must be on a protocol permitted antiretroviral therapy (ART) (See Appendix 10.8 for prohibited concomitant medications) and have a well-controlled HIV infection/disease defined as:
 - a CD4+ T cell count >350 cells/mm³ at time of screening;
 - must have achieved and maintained virologic suppression defined as confirmed HIV RNA level below 50 copies/mL or the lower limit of qualification (below the limit of detection) using the locally available assay at the time of screening and for at least 12 weeks prior to screening;

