10.8. Appendix 8: Prohibited Concomitant Medications That May Result in DDI

The prohibited concomitant medications listed below should not be taken with PF-07265028 for the period of time at least equal to the required washout period listed in the table, and throughout the conduct of the study.

The Pfizer study team is to be notified of any prohibited medications taken during the study. After consulting with the sponsor, the investigator will make a judgement on the ongoing participation of any participant with prohibited medication use during the study.

This list of drugs prohibited for potential DDI concerns with PF-07265028 may be revised during the course of the study with written notification from sponsor, to include or exclude specific drugs or drug categories for various reasons (eg, emerging DDI results for the IMP, availability of new information in literature on the DDI potential of other drugs).

This is not an all-inclusive list. Site staff should consult with the sponsor or designee with any questions regarding potential DDI.

Drug Category	Drugs	Required Washout Period requirement
Strong CYP3A4 Inhibitor	Grapefruit juice or grapefruit/grapefruit related citrus fruits (eg, Seville oranges, pomelos), amprenavir, Boceprevir, ceritinib, clarithromycin, conivaptan, cobicistat (GS-9350), fosamprenavir, itraconazole, indinavir, idelalisib, ketoconazole, lopinavir/ritonavir, LCL161, miconazole, mibefradil, nefazodone, nelfinavir, ritonavir, ribociclib, saquinavir, telaprevir, troleandomycin, telithromycin, voriconazole, posaconazole	10 days or 5 half-lives whichever is longer
Moderate CYP3A4 Inhibitor	Amprenavir, aprepitant, atazanavir/ritonavir, ACT-178882, crizotinib, casopitant, cyclosporine, ciprofloxacin, cimetidine, darunavir, duvelisibm diltiazem, darunavir/ritonavir, delavirdine, dronedarone, erythromycin, fluconazole, fedratinib, fluvoxamine, FK1706, letermovir, GSK2647544, lefamulin, faldaprevir, imatinib, istradefylline, isavuconazole, magnolia vine (Schisandra sphenanthera), netupitant, nilotinib, palbociclib, ravuconazole, tofisopam, voxelotor, verapamil	10 days or 5 half-lives whichever is longer
Strong CYP3A4 Inducer	Apalutamide, avasimibe, carbamazepine, clevipidine, enzalutamide, lumacaftor, mitotane, rifampin, rifabutin, rifapentine, phenytoin, phenobarbital, St John's Wort extract	10 days or 5 half-lives whichever is longer

090177e198aafefApproved\Approved On: 22-Nov-2021 20:52 (GMT)

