Drug Category	Drugs	Required Washout Period requirement
CYP3A4 Sensitive Substrate	Amiodarone, alfentanil (excluding transdermal patch), astemizole, cisapride, cyclosporine, dihydroergotamine, ergotamine, everolimus, fentanyl (excluding transdermal patch), pimozone, quinidine, rifampin, sirolimus, terfenadine, tacrolimus, valproate	10 days or 5 half-lives whichever is longer
CYP2D6 Sensitive Substrate	Desipramine, flecainide, nortriptyline, quinidine, thioridazine, pimozone, trimipramine	10 days or 5 half-lives whichever is longer
UGT1A1 Sensitive Substrate	Belinostat, irinotecan	10 days or 5 half-lives whichever is longer
BCRP Highly Sensitive Substrate	Paritaprevir, pemafibrate	10 days or 5 half-lives whichever is longer
P-gp Sensitive Substrate	Sirolimus, temsirolimus	10 days or 5 half-lives whichever is longer

The following drugs need to be used with caution or lower the dose:

- P-gp substrate: Digoxin (monitoring of serum digoxin level is recommended and dose reduction of digoxin may be needed).
- Statins: Atorvastatin (limit dose to 20 mg daily), fluvastatin (limit dose to 20 mg daily), rosuvastatin (limit dose to 10 mg once daily), simvastatin (limit dose to 10 mg daily).
- BCRP substrates: apixaban, glecaprevir, letermovir, pibrentasvir, rivaroxaban, sofosbuvir, sulfasalazine, tenofovir.
- OCT-1/MATE2K substrate: Metformin.

Investigators should consult the product label for any other medication used during the study for information regarding medication that is prohibited for concomitant use.

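### Section 6.8.1 and Appendix 8 of the protocol set different limits for three of the four statins named, and nothing says which governs

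*Protocol*

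**What the plan says.** Section 6.8.1 of the protocol lists four statins and their limits: "Atorvastatin (limit dose to 10 mg daily), fluvastatin (limit dose to 20 mg daily), rosuvastatin (limit dose to 5 mg daily), simvastatin (avoid usage"). It then sends the reader to Appendix 8 "for a comprehensive list for prohibited drugs or use with caution due to DDI".

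Appendix 8 (Section 10.8) has a table of prohibited drugs, followed by a shorter list of drugs to be used cautiously or at a reduced dose. The statins are in that second list: "Atorvastatin (limit dose to 20 mg daily"), fluvastatin at 20 mg daily, then "rosuvastatin (limit dose to 10 mg once daily), simvastatin (limit dose to 10 mg daily").

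On where instructions are to be found, Section 6.8 says: "Prohibited therapies and concomitant therapy instructions during the study are listed in this section and in the sub-study appendices". It gives no order of precedence.

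**The concern.** These are dose limits for common co-medications in a first-in-human study, and they are there because of a drug interaction the sponsor itself raises. Section 2.2.6 describes PF-07265028 as a possible cause of interactions through several routes, among them "reversible inhibition of CYP3A, UGT1A1, and transporter-mediated inhibition of P-gp, BCRP, and OCT1 at the clinically relevant dose of 140 mg QD". Section 6.8.1 adds that exposure to substrates of CYP3A4, P-gp and BCRP may rise, and the statin limits follow directly after that warning.

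If both texts stand, what a participant may take depends on which page the site staff open. A site working from Appendix 8 alone could keep a participant on twice the atorvastatin or rosuvastatin dose that Section 6.8.1 permits, or on simvastatin that Section 6.8.1 says to avoid. That puts participant safety at risk and makes practice differ between sites.

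**Working it through.** No power, sample-size or error-rate figure is involved. The check sets the two lists side by side and then looks for any text that settles the difference.

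**Step 1: the limits, drug by drug.** Ratio = Appendix 8 cap ÷ Section 6.8.1 cap.

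| Statin | Section 6.8.1 | Appendix 8 | Ratio |
|---|---|---|---|
| Atorvastatin | 10 mg daily | 20 mg daily | 20/10 = 2.0 |
| Fluvastatin | 20 mg daily | 20 mg daily | 20/20 = 1.0 |
| Rosuvastatin | 5 mg daily | 10 mg once daily | 10/5 = 2.0 |
| Simvastatin | avoid | 10 mg daily | none: avoid against allowed |

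Three of the four differ, and Appendix 8 is the more permissive each time.

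**Step 2: is either text superseded or incomplete?** No. Both are in the body of the current protocol, neither is in an amendment log, and neither is redacted.

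**Step 3: does any text give precedence?**

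- Section 6.8 names the section and the appendices together and ranks neither.
- The pointer in Section 6.8.1 calls Appendix 8 comprehensive. It comes straight after the stricter limits, so it leads the reader to the looser ones without saying that they override.
- Exclusion criteria 17 and 18 cite Section 10.8, but they concern CYP3A4 inhibitors and inducers, narrow-index sensitive substrates and highly sensitive BCRP substrates. No statin appears in the Appendix 8 table for those classes, so these criteria do not settle statin doses.
- Exclusion criterion 20 ("Current use of any prohibited concomitant medication(s) or those unwilling/unable to use a permitted concomitant medication(s")) refers to Section 6.8. That leans towards the stricter text for simvastatin, but it is an eligibility rule and sets no dose cap.
- Appendix 8 says that its list of prohibited drugs "may be revised during the course of the study with written notification from sponsor". That is a way to change the list. It does not resolve a conflict with Section 6.8.1.
- Sections 6.8 and 10.8 both invite questions to the sponsor. A site that has read only one list has no reason to ask.
- Section 6.8.1 also cites Appendix 9 for a full drug list, but Appendix 9 holds country-specific requirements. The cross-references in this section cannot be relied on to settle the point.

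**Step 4: can doses reach the level at which interactions are expected?** The provisional levels in Table 7 stop at 125 mg, below the 140 mg named in Section 2.2.6. The Table 7 footnote allows further increments of up to 60% until the MTD or RDE is determined, and 125 × 1.6 = 200 mg. Table 16 lists provisional doses up to 500 mg. Doses above 140 mg are therefore within the plan.

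**The case against.** The strongest reply is that this is a drafting slip with no demonstrated harm. Both texts restrict statin use, and the heading of the Appendix 8 list itself calls for caution or a lower dose. A reading that complies with both exists: follow Section 6.8.1. A site that goes from Section 6.8.1 to Appendix 8 will see both sets of limits and can ask the sponsor. The protocol derives neither set of caps and does not say which enzyme or transporter handles each statin, so nothing in it shows the higher caps to be unsafe. Section 2.2.6 speaks of potential interactions, and all four provisional dose levels lie below 140 mg.

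Much of this stands, and it limits what may be claimed. The factor of 2 compares written caps; it does not measure exposure or harm. The interaction is a nonclinical expectation. An effect on how DLTs are attributed is conceivable, but it cannot be quantified from the documents and is partly guarded against: the Hy's law criterion considers other drugs as a cause, and the final DLT decision is taken at the dose level review meeting. It should carry no weight here.

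None of it removes the contradiction. The existence of a compliant reading does not help a site that opens only Appendix 8, which is the list it is told is comprehensive. The invitation to ask helps only someone who has noticed the discrepancy.

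**Conclusion.** The concern holds. Section 6.8.1 and Appendix 8 conflict on three of the four statins. Two caps differ by a factor of 2.0, and for simvastatin an instruction to avoid becomes an allowance of up to 10 mg daily. Appendix 8 is looser in all three, and no text decides between the sections. The protocol is wrong as written on this point.

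The conclusion rests only on the two current passages and on the absence of a precedence rule. It does not assume that the higher caps are unsafe. The number of participants exposed is unknown because the documents do not report statin use. No endpoint, estimand, decision rule or sample size changes. It should be corrected because it is a contradictory dosing instruction in a first-in-human study and is cheap to put right.

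**What to change.** Set the Appendix 8 statin line to the stricter limits: atorvastatin 10 mg daily, fluvastatin 20 mg daily, rosuvastatin 5 mg daily, and no simvastatin. If the sponsor holds interaction data that support the higher caps, amend Section 6.8.1 instead and give the reason. Either way, state the limits once and have the other section refer to that place. The same amendment can correct the Appendix 9 cross-reference in Section 6.8.1.

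Notify sites in writing without waiting for the next amendment. The notification clause in Appendix 8 is worded for the prohibited-drug list, and statins are in the caution list, so the protocol text should be amended as well.

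The cost is a wording change, one notice to sites and possibly a statin switch or dose reduction for participants already taking more than the Section 6.8.1 limits. How many that would be cannot be told from the documents.

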6.8.3. Supportive Care

Palliative and supportive care for disease related symptoms may be administered at the investigator's discretion and according to the specific supportive care product Prescribing Information or the current ASCO guidelines.⁵⁰

6.8.3.3. Supportive Care for Immune-Related Adverse Events

For immunotherapeutic agents, treatment of irAEs is mainly dependent upon severity (NCI CTCAE grade version 5.0). In general, Grade 1 or 2 irAEs are treated symptomatically with persistent Grade 2, Grade 3 or Grade 4 irAEs managed with moderate to high corticosteroids.

Guidelines for the management of irAEs are provided in [Appendix 3, Section 10.3.5](#).

6.8.4. Hematopoietic Growth Factors

Primary prophylactic use of colony stimulating factors is not permitted during the first 28 days of Cycle 1 Part 1, but they may be used to treat treatment-emergent neutropenia as indicated by the current ASCO guidelines.⁵²

For Japan only: since the indication and dosage of G-CSF compounds approved in Japan may differ from ASCO guidelines, please refer to Japanese package insert.

Erythropoietin may be used at the investigator's discretion for the supportive treatment of anemia. Erythropoietin is not approved in some countries, including Japan, for anemia caused by cancer treatment.

6.8.5. Antidiarrheal, Antiemetic Therapy

Primary prophylaxis beyond the first cycle is at the investigator's discretion. The choice of the prophylactic drug as well as the duration of treatment is up to the investigator with sponsor approval assuming there is no known or expected drug-drug interaction and assuming the drug is not included in the Concomitant Therapy section ([Section 6.8](#)).

6.8.6. Corticosteroids

Chronic systemic corticosteroid use (prednisone >10 mg/day or equivalents) for palliative or supportive purposes is not permitted. Acute emergency administration, topical applications, inhaled sprays, eye drops, or local injections of corticosteroids are allowed.

6.8.7. Anti-Inflammatory Therapy

Anti-inflammatory or narcotic analgesic may be offered as needed assuming there is no known or expected drug-drug interaction and assuming the drug is not included in the Concomitant Therapy section ([Section 6.8](#)).

6.8.8. Proton pump inhibitors, Antacids or H2-Receptor Antagonists

In the absence of in vitro data evaluating the PF-07265028 solubility in acidic pH, participants are prohibited from using acid reducing agents as described below:

- a. Patient should not use proton pump inhibitors, eg, omeprazole, esomeprazole, lansoprazole, pantoprazole, rabeprazole, or dexlansoprazole, at least 7 days prior to C1D1 and throughout the study.
- b. When concurrent use of an H2 blocking agent is necessary, eg, ranitidine, famotidine, or cimetidine, it must be administered only between 2 and 3 hours after the dose of PF-07265028. If not taken during this time, the dose of H2 blocking agents should not be taken again until 2–3 hours after the next dose of PF-07265028.
- c. When concurrent use of an antacid is necessary, eg, aluminum hydroxide/magnesium hydroxide/simethicone or calcium carbonate, it must be administered 2 or more hours before and/or 2 or more hours after the dose of PF-07265028.

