4.3.3. DLT Definition

A participant is classified as DLT-evaluable if the participant either 1) received at least 75% of the planned doses of the study intervention and have received all scheduled safety assessments during the DLT-observation period (Cycle 1 [28 days]) or 2) have experienced a DLT regardless of the percentage of planned doses received. The percentage of drug received is calculated as the percentage of the actual total amount of drug(s) administered during the DLT-observation period in relation to the planned total amount of drug(s) to be administered for the DLT-observation period. If a participant fails to meet these criteria, the participant is deemed non-evaluable for a DLT, and may be replaced. The sole exception to criterion 1 above is if the participant has missed a minority of safety assessments due to emergency situations (eg, site accessibility issues, inability to go to an external lab, etc). In such cases, the DLRM Committee may judge the participant evaluable, depending on the abundance of the available data.

For the purpose of dose escalation, all treatment-emergent AEs meeting the definition of DLT occurring in the first cycle of treatment (within 28 days of the first dose or until the participant receives the first dose of the second treatment cycle in the event of treatment delays) will be considered DLTs unless they are clearly attributable to underlying disease or intercurrent illness.

Severity of AEs will be graded according to CTCAE version 5.0. For those AEs involving a worsening of a baseline abnormality, a DLT must represent a clinically significant (in the opinion of the Investigator after discussion with the sponsor) shift from baseline.

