9.2. Analysis Sets

For purposes of analysis, the following analysis sets are defined.

Participant Analysis Set	Description
FAS	All enrolled participants who have been assigned to treatment. Participants are analyzed according to the treatment they were assigned.
SAS	All enrolled participants who receive at least 1 dose of study treatment. Unless otherwise specified the safety analysis set will be the default analysis set used for all analyses.
Per-Protocol Analysis Set (DLT-Evaluable Set)	All enrolled participants who had at least 1 dose of study treatment and either experienced DLT or do not have major protocol deviations during the DLT observation period.
mITT Population	All enrolled participants who have received at least 1 dose of study medication; have a baseline assessment and at least 1 post-baseline assessment.
PK Parameter Set	All enrolled participants treated who do not have protocol deviations influencing PK assessment, and have sufficient information to estimate at least 1 of the PK parameters of interest.
PK Concentration Set	All enrolled participants who are treated and have at least 1 analyte concentration above the lower limit of quantitation.
Response Evaluable Set	All enrolled participants who received at least 1 dose of study treatment and had adequate baseline disease assessment. Participants who discontinued early or died will be included.
Pharmacodynamic/ Biomarker Analysis Sets	The Pharmacodynamic/Biomarker analysis population is defined as all enrolled participants with at least 1 of the Pharmacodynamic/Biomarkers evaluated at pre- and/or postdose.
Immunogenicity Analysis Set	The immunogenicity analysis set is a subset of the safety analysis set and includes participants who have at least 1 analyzed sasanlimab ADA/NAb sample.

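### Protocol Section 6.8.8(b) names cimetidine as a usable H2 blocker, while Appendix 8 prohibits it throughout the study as a moderate CYP3A4 inhibitor

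*Protocol*

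**What the plan says.** Section 6.8.8 bars proton pump inhibitors, then gives conditions under which H2 blockers and antacids may be used. Item (b) begins "When concurrent use of an H2 blocking agent is necessary, eg, ranitidine, famotidine, or cimetidine" and allows the drug only in the window 2 to 3 hours after a PF-07265028 dose. The stated reason for the whole section is the lack of in vitro solubility data in acidic pH.

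Appendix 8 (Section 10.8) tabulates drugs prohibited for interaction reasons. Its moderate CYP3A4 inhibitor row contains the run "cyclosporine, ciprofloxacin, cimetidine, darunavir". The appendix gives the duration of the ban on every drug in the table as "for the period of time at least equal to the required washout period listed in the table, and throughout the conduct of the study".

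Three other places bear on the conflict:

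- Exclusion criterion 17 (Section 5.2) excludes current or anticipated use of agents "that are known strong and/or moderate CYP3A4 inhibitors, or strong CYP3A4 inducers, including their administration within 10 days or 5 half-lives" and refers to Section 10.8 for the list. It does not name cimetidine.
- Section 6.8.1 says use of such inhibitors "is prohibited within 10 days or 5 half-lives of the CYP3A4 inhibitor/inducer (whichever is longer) prior to the first dose of study intervention". It first sends the reader to Appendix 9 for the list, and its last sentence cites Appendix 8.
- Section 2.2.6 gives the reason the restriction matters: "The major route of clearance for PF-07265028 is predicted to be CYP3A4-mediated oxidative metabolism", with a fraction metabolized by CYP3A of 0.80.

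**The concern.** Both texts name the same drug, so this is not a general rule with a specific exception. One permits cimetidine on condition of timing; the other forbids it outright. A site that opens the acid-reducer section to choose an H2 blocker would find cimetidine offered there.

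At stake is exposure to PF-07265028 during first-in-human dose finding. Section 6.8.1 itself recognizes that CYP3A4/5 inhibition may raise exposure and toxicity. If that led to a Cycle 1 toxicity, the event could be charged to the assigned dose. Under Section 4.3.3, qualifying events "will be considered DLTs unless they are clearly attributable to underlying disease or intercurrent illness", and a drug interaction is neither of those. The DLT-evaluable set in Section 9.2 keeps participants who "either experienced DLT or do not have major protocol deviations during the DLT observation period", so a participant with a DLT stays in even if the cimetidine use is recorded as a major deviation. The BLRM would then read the event as information about the nominal dose.

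**Working it through.** The plan states no figure on this point, so the main check is a comparison of texts. A short illustration of scale follows.

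**Do the texts conflict?**

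| Question | Section 6.8.8(b) | Appendix 8 |
|---|---|---|
| Is cimetidine named? | Yes, as an example of an H2 blocker | Yes, in the moderate CYP3A4 inhibitor row |
| May it be taken on study? | Yes, when necessary | No |
| Condition | 2 to 3 hours after PF-07265028 | None; the ban covers washout and the whole study |
| Reason | Solubility and stomach pH | CYP3A4 interaction |

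**Can the two be reconciled?**

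1. The opening of Section 6.8.8 is phrased as a prohibition, but only in the terms of its items, and item (b) describes permitted use.
2. The timing window answers the pH question. It says nothing about CYP3A4, so meeting it does not meet Appendix 8.
3. Sections 6.8.5 and 6.8.7, on antidiarrheals/antiemetics and on anti-inflammatories, make use conditional on no known or expected drug interaction. Section 6.8.8 has no such condition.
4. Section 6.8.1 does not settle it. Its inhibitor ban is worded only as a washout before the first dose, and the appendix it first cites for the list, Appendix 9, holds country-specific (Japan) requirements.
5. Exclusion criterion 17 is an eligibility rule. It does not clearly govern an H2 blocker started mid-study under Section 6.8.8.
6. Appendix 8 lets the investigator, after consulting the sponsor, judge whether a participant who took a prohibited drug continues. That deals with a breach; it does not permit the use.

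No reading of the current text satisfies both provisions for cimetidine.

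**How large could the exposure change be?** The documents do not say. As an illustration, let f be the share of total clearance through CYP3A and I the fraction of that pathway inhibited. Then

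exposure ratio = 1 / (1 − f × I).

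Inputs: f = 0.80, taking the Section 2.2.6 value as a share of total clearance. I = 0.25 and 0.50 are assumptions. A second case assumes that metabolism is 90% of total clearance, giving f = 0.80 × 0.90 = 0.72.

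| f | I (assumed) | Calculation | Exposure ratio |
|---|---|---|---|
| 0.80 | 0.25 | 1 / (1 − 0.20) | 1.25 |
| 0.80 | 0.50 | 1 / (1 − 0.40) | 1.67 |
| 0.72 | 0.25 | 1 / (1 − 0.18) | 1.22 |
| 0.72 | 0.50 | 1 / (1 − 0.36) | 1.56 |

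For comparison, Section 4.1.1 caps dose increments beyond DL2 at 60%, a ratio of 1.60. If exposure were proportional to dose (a further assumption), the upper end of this range would be about one full dose step. These figures follow from the assumed I and are not evidence of what cimetidine would do.

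**The case against.** The strongest reply is that a careful site would not be misled. Exclusion criterion 17 bars anticipated need for moderate CYP3A4 inhibitors, and criterion 20 bars current use of prohibited medication. The last sentence of Section 6.8.1 points to Appendix 8. Section 6.8 and Appendix 8 both send questions to the sponsor. Section 6.8.8 does not claim to override the interaction list, so reading the rules together and applying the stricter is natural, and famotidine or ranitidine would serve. This stands as a reason to expect few cases. It leaves in place an instruction that names a prohibited drug as usable.

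The second reply concerns DLT attribution. Section 4.3.3 is not the whole rule. Section 4.3.3.2 has alternative-cause conditions for Hy's Law and Grade 5 events, and Section 4.3.3.3 lists events that are not adjudicated as DLTs. Section 10.11.3 allows equivocal DLTs a weight of 0.5 in a sensitivity analysis that may become the primary method. SAP Section 6.1.1 leaves the final determination to the investigators and sponsor at the dose level review meeting. So a confounded event can be discounted. None of these provisions expressly covers drug interactions, however, so the event could still count in full.

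Third, detection is likely. Concomitant medication is reviewed at study visits (Table 1), and Part 1 has serial PK sampling on Cycle 1 Days 1 and 15 (Table 2). SAP Section 5.3.3.2 allows participants with events affecting PK to be left out of the PK analysis. This is why the concern is confined to safety and DLT attribution.

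Finally, the clearance route is predicted and the text says inhibition may raise exposure; there were no human data. That is correct, and the exposure figures should carry no weight beyond illustration.

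**Conclusion.** The inconsistency is real and can be read directly from the current protocol: cimetidine is offered in Section 6.8.8(b) and prohibited throughout the study in Appendix 8, with nothing to say which governs. It is wrong as written and it is a safety instruction.

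Its weight is minor. It concerns one drug in a list of examples, alternatives are named beside it, several other clauses point to the prohibition, and no sample size, prior, escalation rule or planned analysis changes. The consequence claimed is limited: a site following Section 6.8.8 could increase PF-07265028 exposure, and a resulting Cycle 1 toxicity could be counted against the assigned dose. That rests on the protocol's own prediction that CYP3A4 is the main clearance route. The size of any increase is not established by the documents.

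**What to change.** In Section 6.8.8(b), delete cimetidine from the examples, keep ranitidine and famotidine, and add that any H2 blocker listed in Appendix 8 remains prohibited. In Section 6.8.1, state that the ban on strong and moderate CYP3A4 inhibitors applies during treatment as well as before the first dose, and change the Appendix 9 reference to Appendix 8.

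One clerical item can be tidied in the same edit: letermovir appears both in the prohibited moderate-inhibitor row of Appendix 8 and in its use-with-caution list under BCRP substrates. Remove it from the caution list. No separate consequence is claimed for it.

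The cost is protocol wording only.
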